#### **4.4 Screening for eligibility**

The HCRF Research Nurse (or UoA researcher for MBO participants) will contact the mother at the agreed time and run through the HADS with her. The HADS scores will be automatically generated within the eCRF so the Research Nurse can let potential participants know their score right away. If the participant scores above threshold on either subscale ( $\geq 11$  HADS-A;  $\geq 7$  HADS-D) the Research Nurse will then check the other eligibility criteria. If the mother is

still interested in taking part, arrangements will be made for obtaining informed consent and baseline measures.

#### **4.5 Informed consent**

The Research Nurse will visit the mother at a pre-arranged mutually convenient time at her home. At the home visit the study's PIL will be discussed and the mother's questions answered. Then, if the mother wishes to proceed, written informed consent to participate in the trial will be obtained. Baseline measures will be taken either at this initial visit or at a subsequent visit according to the mother's preference. This will include completing questionnaires and taking a video of a mealtime or other interaction between the mother and child (although the video aspect is optional). Consent will be sought for contact details to be collected for two informants who would be likely to stay in touch with participating mothers, so that they could be contacted if tracing proves difficult during follow up. These informants will be sent a 'best contact' letter describing the intended use of their information and giving the opportunity to opt out.

The following amendments have been made to the consent form:

- Participant also agrees to their Health Visitor being informed of their participation in the trial
- Participant has the option to also give consent to provide an anonymised vignette of their opinion of the trial and their participation in it.

For MBO add-on study participants – the UoA Researcher will send out a Participant Information Sheet (PIS) and consent form prior to a phone call with the potential participant. The researcher will talk through the PIS and answer any questions the participant may have. If the participant is happy to proceed, the researcher will read through each statement on the consent form and seek verbal consent from the potential participant. The researcher will also ask the participant to fill in the consent form electronically (entering their initials against statements and including their full name and the date of consent) and send it back to the research team via their personal email. The researcher will sign the consent form and send a completed copy for the participant to keep. A copy of the consent form will also be kept in the study's electronic site file on a secure UoA server. A UoA researcher will arrange a phone / video call with the participant to complete the baseline questionnaires.

#### **4.6 Randomisation and allocation**

The Research Nurse will use the online randomisation service (provided by the Trial Office) to randomise the participant, the consent / baseline home visit. A random element will be incorporated into the randomisation algorithm. Eligible and consenting participants are randomised to either the intervention (MB) or control (UC) group using the proven 24-hour web-based application hosted by CHaRT. The Research Nurse will contact the mother, by telephone, and inform her of the randomisation result. The Chief Investigator, Co-Investigators and administrative staff will be blinded to the randomisation result. We shall use a minimisation design to reduce imbalance between groups in terms of maternal age (<25; ≥25 years), deprivation (working household yes/no) and age of child (≤12 months; >12 months).

For MBO add-on study participants, randomisation will be conducted immediately following baseline measures by the UoA researcher during the baseline phone / video call using the same web-based application hosted by CHaRT. During this call the participant will be informed of which study arm they have been allocated to. The UoA researcher will inform the intervention team (at Mellow Parenting) of participants randomised to receive the intervention once the group is adequately populated. The UoA researcher will send the name and contact details of all consenting intervention participants to Mellow Parenting (one file per group via Zend-To file transfer) prior to the group start date. The Chief Investigator, Co-Investigators and project staff involved in outcome assessment will be blinded to the study arm allocation.

The maximum time allowable from randomisation to intervention commencement will be 3 months or if the baby reaches 18 months of age before the next available group commences. If a participant reaches 3 months of waiting time and her baby is still younger than 18 months

(and the mother is still keen to participate), the HADS will be re-administered to confirm eligibility.

#### **4.7 Code break/Emergency unblinding procedures**

There is no requirement for emergency unblinding procedures. This is because knowledge of whether a participant is in the control or intervention group will not alter any management decisions should an adverse event occur.

#### **4.8 Administration arrangements post recruitment**

The UoA Trial Team will be responsible for the following:

- Notify the GP (if consent given) in writing when a patient of theirs has consented to participate in the Mellow Babies Study. A summary of the trial will be included on the back of the GP letter.
- Send Letter to Best Contact to gain consent to contact if we are having difficulty reaching the participant for follow-up.

The Clinical Research Nurses in the HCRF will be responsible for the following:

- Notify referrers (if consent given) in writing that a participant has consented to participate in the Mellow Babies Study and their randomisation result.
- Enter trial data regarding the participant into the study website secure data portal.
- Maintain trial documentation at site.
- Return a copy of the signed consent form to the CRH.
- Ensure the signed informed consent form is filed within the Investigator Site File (kept electronically on the trial website and any paper copies within the CRH)
- Provide a point of contact for participants and Mellow Babies Intervention facilitators.

We intend to produce a yearly Newsletter for participants and collaborators to inform everyone of progress and maintain enthusiasm.

## **5. OUTCOME MEASURES**

### **5.1 Primary outcome measure**

Maternal self-complete HADS (57) at eight months post randomisation and when children are 30 months old.

### **5.2 Secondary outcome measures**

#### **At 8 months post-recruitment:**

- Maternal HADS
- SSLM
- Brief Infant-Toddler Social and Emotional Assessment (BITSEA) (63-65)
- Caregiver accounts of the experience of interventions
- Participants' service use and out of pocket expenses
- Mothers' quality of life as measured by EQ-5D-5L
- Positive and negative parenting behaviours during a videoed family meal using the Mellow Parenting Observational System (MPOS) (2).

#### **At 30 months of age:**

- Social and emotional functioning as measured by the total difficulties scale of the maternally-reported SDQ (66) at age 30 months (15). We have recently published work on the predictive validity of the SDQ at this age (48).

- Emotional, conduct, hyperactivity/inattention and peer relationship problems, and prosocial behaviour (SDQ subscale scores).
- Expressive language performance in the 50-word Sure Start Language Measure (67) (SSLM). There is a substantial overlap between language delay and psychopathology (13, 15). We have recently reported excellent predictive validity for language disorder and global cognitive impairment (48). Parent completion questionnaire.
- The Bayley III Scales of Infant and Toddler Development (68) including Behavior Observation Inventory. Assessment by research assistant with some input by parental caregivers. The Ages and Stages Questionnaire 3 and Social and Emotional 2 where face-to-face observation is prohibited – this is a questionnaire measure completed by the parent and then reviewed over the phone with the researcher. OBJECTIVELY objectively
- Positive and negative parenting behaviours during a videoed family meal using the Mellow Parenting Observational System (MPOS) (2).
- Within-trial cost analysis of participants' service use and out of pocket expenses
- Cost-consequence analysis of the MB intervention vs usual care
- Mothers' quality of life as measured by EQ-5D-5L
- Satisfaction with intervention / usual care

Objective assessments will include the Bayley III scales at 30 months (where permitted). Raters blinded to allocation will assess mealtime videos.

### 5.3 MBO add-on study outcome measures

We have tailored the measures included in the MBO study based on those likely to be sensitive to change over a much shorter period (i.e. parental wellbeing rather than child development).

#### Primary outcome measure:

- Maternal self-complete HADS within 1-month post-participation

#### Secondary outcome measures (within 1-month post-participation):

- Parental Stress Index (PSI-4-SF)
- Parental Sense of Competence Scale (PSOC)
- The Parental Reflective Functioning Questionnaire (PRFQ)
- Mothers' Quality of Life as measured by EQ-5D-5L
- Positive and negative parenting behaviours during a videoed family meal using the Mellow Parenting Observational System (MPOS)

## 6. DATA COLLECTION AND PROCESSING

### 6.1 Measuring outcomes

Table 1 (below) summarises required research activities and visit timepoints. Further details about collection of outcome data are provided elsewhere in this section.

**Table 1**

Contact	Screening Telephone	Consent Home Visit	Baseline Visit ( may be combined with Consent Visit )	(Intervention arm) MB Intervention wks 1-14 1 day weekly	8 mths Post randomisation	Child 30 mths	End of Study
Consent	✓	✓					
Maternal HADS	✓				✓	✓	
BITSEA			✓		✓		
SSLM					✓	✓	

SDQ						✓	
EQ-5D-5L			✓		✓	✓	
Bayley III / ASQ 						✓	
Socio-demographic questionnaire			✓				
Video interaction			✓		✓	✓	
Maternal account of service					✓	✓	
Participant Cost Questionnaire					✓	✓	
Attend Mellow Babies Intervention				✓			
Contact with study results							✓

## 6.2 Baseline

Baseline measures will be the HADS (taken at screening stage), the Brief Infant-Toddler Social and Emotional Assessment (65) (BITSEA), the EQ-5D-5L and a video of parent-child interaction during a mealtime obtained from those families who will accept it, all administered by HCRF Research Nurses along with a brief demographic questionnaire. The demographic questionnaire will record ethnicity, age at leaving school, educational qualification level, employment status, socioeconomic status, household composition, substance use, obstetric history, social support (including partner support), and views on parenting support and confidence. All participants will be offered a £10 voucher for completion of baseline visit.

## 6.3 Follow-up

Participants are contacted by phone, post or email as appropriate. In case of non-attendance at follow-up appointments or non-return of questionnaires, attempts are made by HCRF staff or staff at UoA CRH Research Office to trace the participant directly using these means, through previously provided contacts or indirectly by contacting the GP.

To maintain contact throughout the trial, the study office will contact families on the birthdays of participating children by sending a card and a small gift (e.g. a small teddy bear with a study logo).

All participants will be offered a £10 voucher for completion of each follow-up visit.

It should be noted that for both follow-up points (8-months post randomisation and when the child is 30-months of age) these follow-ups will ideally be carried out face-to-face in the mother's home. However, follow-up visits may also be carried out remotely. It should be attempted to maintain some form of face-to-face contact (e.g., to use skype or video call); however, if this option is not available then follow-up visits can be carried out over the phone. Researchers will be instructed to take participants through the questionnaires and complete the answers on the participant's behalf. Therefore, this will ensure 100% completion rate of questionnaire data.

### Visit at 8 months Post Randomisation

A UoA Researcher will contact the mother to arrange a home visit and will attend this home visit with a second member of staff from HCRF or UoA. Required at this visit are a maternal HADS

 The ASQ will be used when it is not possible to conduct in-person assessments (i.e due to Covid-19 restrictions.)

(Hospital Anxiety and Depression Scale), SSLM (Sure Start Language Measure), BITSEA (Brief Infant-Toddler Social and Emotional Assessment), maternal quality of life (EQ-5D-5L).

If the mother has consented, a video of the mother and child together will be recorded (in a caregiving situation, ideally a mealtime). If the mother has consented, a video of the mother and child together will be recorded (in a caregiving situation, ideally a mealtime). In the event of a nurse/researcher being unable to come and film the participant in their home, the participant will be asked if they would be willing to complete their own recording and to send this securely to the research team via the University's ZendTo platform.

The Participant Cost Questionnaire (PCQ) will be completed to ascertain service use and any out of pocket expenses. It should be noted that the PCQ was edited as part of AM015. At 8-month post-randomisation participants are asked Part A of the questionnaire (service use), but not Part B (travel and time) to reduce respondent burden. The recall period here is 'in the last 8-months'.

Follow-ups at 8-months post randomisation must be completed within 28 days of the participant's randomisation date.

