#### **3.1 Intervention being evaluated**

Mellow Babies (MB) is a group for mothers who are having difficulties in their relationship with their baby. The groups look at mothers' feelings of wellbeing (depression, anxiety, stress, etc). It also looks at the way mothers interact with their baby and aims to improve both. The MB programme involves attendance on 14 consecutive weeks within school hours and there is a reunion 1-3 months later. Groups can be offered at weekends, and transport (or transport cost), meals and a crèche are provided. MB aims to enhance close parent-infant attunement directly using a combination of video feedback and hands-on practice in baby-massage, interaction coaching and infant-focussed speech. Video material of a mealtime is shared, (34) and mothers are encouraged to discuss solutions to parenting difficulties. The MB programme has been used widely throughout the UK and internationally: over 2,000 practitioners have been trained and many thousands of families have participated. It has been used with women suffering postnatal depression and other social and psychological difficulties (52) and retention figures are high, even among those facing the greatest adversity.

Our pilot work found that video and audio recording for fidelity monitoring is unacceptable. Practitioner logs and records from supervision sessions will be used for this purpose.

The interventions will be carried out by experienced HCRF staff from a range of professional backgrounds who have worked with groups and who have received training in the MB intervention. The training to be provided to these staff lasts for three days. A key component of the MB programme is the need for expert supervision of the group facilitators by a psychologist. These supervision sessions, lasting 2 hours, will be provided monthly (i.e., three during the 14-week course of each group) by the Mellow Parenting organisation for all participating personnel, generally by Skype or videoconference, following strict confidentiality procedures.

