### Visit when Child is 30 months of Age

A UoA researcher will contact the mother to arrange a home visit and will attend this home visit with a second member of staff from either HCRF or UoA. Required at this visit are a maternal HADS, SSLM, Strengths and Difficulties Questionnaire (SDQ) and maternal EQ-5D-5L assessments. In addition the Bayley III Scales of Infant and Toddler Development including Behavior Observation Inventory Assessment will be done with some input by parental caregivers.

Where the ASQ-3 + ASQ:SE-2 must be employed in place of the Bayley III, the participant will complete the questionnaire and responses will be reviewed over the phone with the researcher. Participants will be sent a copy of the ASQ-3, ASQ:SE-2 and SSLM in advance of their 30-month follow-up, so that they are able to try the activities with their child before they review them with the researcher. They will also be sent a copy of the HADS and the SDQ so that they have it for reference during the follow-up call. If the follow-up is not completed by the time the child is 31 months and 15 days, we will use a version of the ASQ-3 suitable for children aged between 31 months 16 days to 34 months 15 days (inclusive). Similarly, if the follow-up is not completed by the time the child is 33 months, we will use a version of the ASQ-SE suitable for children between 33 and 41 months of age. Follow-up assessments when the child is 30-months of age must be completed by the time the child is aged 34 months and 15 days. If the follow-up is not completed by this time, it will be recorded as missing data.

If the mother has consented, a video of the mother and child together will be recorded (in a caregiving situation, ideally a mealtime). In the event of a nurse/researcher being unable to come and film the participant in their home, the participant will be asked if they would be willing to complete their own recording and to send this securely to the research team via the University's ZendTo platform. They will be sent detailed instructions about how to record and submit their video.

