## **20.2 Revised analysis plan – close down**

All outcome analyses in relation to effectiveness of the intervention listed in Section 2 will no longer be conducted. Characteristics of the sample at baseline, follow-up 1 and follow-up 2 will be presented descriptively. We shall also complete some subgroup comparisons based on a revised set of questions (see below).

Process evaluation data will be collected up until the end of March 2023 and analysis in relation to process evaluation questions (see Section 2) will proceed as originally planned (except for those questions pertaining to effectiveness). Thus, the process evaluation questions are now:

- Which eligible mothers agree and which decline to participate in the intervention, and what reasons do they give?
- Which recruitment methods were most effective and was there any variation in participant characteristics with means of recruitment?
- How do sociodemographic characteristics and maternal mental health at baseline relate to:
  - level of participation in MB?
  - group composition?
  - changes in parenting behaviours?
  - maternal mental state at 8m post-recruitment?
  - child development at 30m, using ASQ rather than Bayley
  - whether recruited pre-pandemic (to March 2020) or post (since Nov 2021)?
- What is the nature of usual care offered to participants?
- How do participants describe their experience of participating in MB, which elements of the intervention are considered most influential, and is participation stigmatising?
- Are there family characteristics associated with greater adherence to MB?
- Are there family characteristics associated with greater retention to follow-up?
- How are the features (in terms of process and outcomes of care) of MB valued by mothers?
- What contextual factors facilitate or hinder delivery of, and engagement with, MB?
- What specific impact did the COVID-19 pandemic have on the ability to run intervention groups and the trial

These added / alternative analyses will contribute to understanding of how to recruit underserved populations to trials, as well as whether any baseline information about participants indicates who is likely to complete participation in the intervention (where relevant) and the trial itself.

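### The 28-day window for the 8-month follow-up is counted from randomisation, so it closes about 7 months before the visit is due and no visit made at 8 months can meet it

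*Protocol*

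**What the plan says.** The rule is in Section 6.3, under the 8-month visit: "Follow-ups at 8-months post randomisation must be completed within 28 days of the participant's randomisation date". It is current body text, and no other part of the protocol gives a different window for this visit.

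The rest of the protocol places the visit at 8 months. Section 5.1 defines the primary outcome as "Maternal self-complete HADS (57) at eight months post randomisation and when children are 30 months old". Section 2, Table 1 and the opening of Section 6.3 agree, and Table 1 puts the visit after the intervention weeks. The same subsection as the rule says of the cost questionnaire: "The recall period here is 'in the last 8-months".

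Two other places fix the timing of the programme. Section 3.1: "The MB programme involves attendance on 14 consecutive weeks within school hours". Section 4.6: "The maximum time allowable from randomisation to intervention commencement will be 3 months". Section 3.1 adds a reunion 1 to 3 months after the weekly sessions.

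The rule for the later visit reads differently: "Follow-up assessments when the child is 30-months of age must be completed by the time the child is aged 34 months and 15 days", and then "If the follow-up is not completed by this time, it will be recorded as missing data".

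The close-down plan still uses the 8-month data. Section 20.2 says: "Characteristics of the sample at baseline, follow-up 1 and follow-up 2 will be presented descriptively". It also keeps questions on maternal mental state at 8 months and on retention to follow-up. Section 20.3 keeps 8-month EQ-5D-5L utilities, QALYs, questionnaire completion rates and resource use.

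**The concern.** The window is tied to the wrong date. A limit of 28 days after randomisation cannot apply to a visit due 8 months after randomisation.

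Three things follow.

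- **Deviations.** The rule is worded as mandatory, and Section 14.1 requires deviations to be documented on a breach form. Read literally, every correctly timed 8-month visit is a deviation.
- **The intended window cannot be read from the text.** It may allow lateness only, or 28 days on either side of the due date. Two people building the follow-up 1 dataset could classify the same visit differently.
- **The retained summaries need a working definition of an 8-month visit.** Retention and completion depend on what counts as a completed visit. Resource use depends on timing as well. To illustrate with an assumed date, a visit at month 11 using an 8-month recall would miss the first 3 months after randomisation.

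**Working it through.** The 28 days is a stated rule and not a derived figure, so there is no calculation of the protocol's to reproduce. The check is date arithmetic.

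**Inputs**

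- Written limit: day 28 after randomisation (Section 6.3, 8-month visit).
- Due time: 8 months after randomisation (Sections 2 and 5.1).
- Longest wait to the start of the group: 3 months (Section 4.6).
- Length of the weekly programme: 14 weeks (Section 3.1).
- Reunion: 1 to 3 months after the weekly sessions (Section 3.1).
- Assumption: one month = 365.25 / 12 = 30.44 days.

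**Step 1: when the visit is due.** 8 × 30.44 = day 243.5. Counted on the calendar over all start dates from 2019 to 2022, the range is day 242 to day 245.

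**Step 2: how early the window closes.** 243.5 − 28 = 215.5 days, and 215.5 / 30.44 = 7.1 months. Over the calendar range the gap is 214 to 217 days, or 7.0 to 7.1 months.

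**Step 3: the window against the weekly programme.**

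- Earliest possible end, for a group starting on the day of randomisation: 14 × 7 = day 98.
- End after the longest routine wait: 3 × 30.44 + 98 = 91.3 + 98 = day 189.3.

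Day 28 comes before both, so the written window always closes before the weekly sessions end.

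**Step 4: the two plausible readings if the 28 days run from the due date.**

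| Reading | Opens | Closes |
|---|---|---|
| Up to 28 days late | day 243.5 | day 271.5 |
| 28 days either side | day 215.5 | day 271.5 |

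Both close at 243.5 + 28 = day 271.5. They differ only in whether a visit in the 28 days before the due date counts as in window.

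**Step 5: the re-anchored window against the whole programme.** Both readings open after day 189.3, when the weekly sessions end following the longest routine wait. The reunion is another matter: after that wait and a 3-month interval it falls at 189.3 + 91.3 = about day 281, later than day 271.5. The separation therefore holds for the weekly sessions only.

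**The case against.** The strongest reply is that this is an obvious slip. The heading, the recall period, the primary outcome and Table 1 all show a visit at 8 months, and nobody could plausibly carry it out by day 28. The effectiveness analysis has been cancelled, and Section 20.1 says the final phase of close-down involves no follow-up assessments, so the sentence will govern few or no further visits. No comparison between arms now depends on it. All of this stands and limits the consequence. It does not make the rule workable or show which window was meant.

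A reader might go further in five ways that the protocol does not support.

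- **That no 8-month record is valid.** No consequence is attached to an out-of-window 8-month visit. Only the 30-month visit has a rule recording late assessments as missing. The lack of such a rule at 8 months is not itself a fault, since out-of-window handling is commonly left to the SAP.
- **That very late contacts after the COVID pause are pooled with on-time ones.** Section 9.2 describes a pause in recruitment, and Section 6.3 permits remote follow-up. No visit dates are given.
- **That day 28 usually falls before the group starts.** Section 4.6 gives a maximum wait and no distribution of waiting times.
- **That a corrected window lies wholly after the programme.** The reunion can fall later.
- **That late 8-month records should now be set to missing, as at 30 months.** The 30-month cut-off coincides with the upper age limit of the ASQ-3 version used, and no such limit is given for the 8-month measures. Section 6.4, writing about withdrawal, says collected data are kept and used unless consent for that is withdrawn. Discarding observed records would cut against this in a trial already underpowered.

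**Conclusion.** The point holds as an error in a mandatory rule. As written, the 8-month window closes 214 to 217 days, about 7 months, before the visit is due and before the weekly programme can end. No visit made at 8 months can meet it.

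The consequence is limited to deviation reporting and to the retained 8-month summaries: sample characteristics, maternal mental state, retention, completion, EQ-5D-5L and QALYs, and resource use. No treatment-effect estimate is affected, because none is now planned.

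The size of the gap rests only on calendar arithmetic. That the 28 days was meant to run from the 8-month date is an inference, though a strong one. Whether it was meant to run in one direction or both cannot be settled from the protocol. How many records fall outside either window is unknown, because no visit dates are given.

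**What to change.** Replace the sentence so that the 28 days are counted from the date 8 months after randomisation. The sponsor should confirm from trial records whether the window allows lateness only or runs on both sides, and state which. The latest completion is about day 271 in either case.

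Then, for the follow-up 1 dataset:

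- apply the corrected window when the dataset is built;
- keep out-of-window records and flag them, without setting them to missing;
- report the actual timing of 8-month visits and the number out of window;
- add a sensitivity summary restricted to in-window visits.

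The cost is one corrected sentence and a modest date check on existing records. Some visits may be flagged as out of window, but no observed data are lost.
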